### **Study Purpose and Rationale**

The prevalence of obesity and associated metabolic diseases continues to rise yet effective non-surgical long-term treatments remain elusive. The success of dieting can be enhanced by pharmacological treatment. However considerable individual variability is observed in response to pharmacotherapy and there is no way to predict who will respond well to a given medication. Peripheral metabolic signals, including leptin and insulin, communicate levels of energy stores to key brain regions and elicit a host of neuronal responses that maintain energy balance; such regulatory mechanisms make it difficult to maintain diet-induced weight loss. The overall research objective is to characterize these mechanisms and to determine how they are impacted by pharmacotherapy in order to predict who will or will not respond to a given weight loss medication. Studies will focus on the melanocortin neuronal system, consisting of the proopiomelanocortin (POMC)-derived MSH peptides, the MSH antagonist, agouti related protein (AgRP) and brain melanocortin receptors, that plays a critical role in responding to these peripheral signals and maintaining energy balance (1). This protocol will focus on the weight loss drug lorcaserin (LOR) a serotonin (5HT2c) receptor agonist, as it works primarily by activation of POMC neurons and brain melanocortin signaling. POMC neurons express 5-HT2cR and are activated by 5-HT agonists (2) In addition, the obesity phenotype of the global 5-HT2cR KO mouse can be normalized by selective 5-HT2cR expression only in POMC neurons (3). Furthermore the feeding effects of 5-HT agonists are abolished by genetic inactivation of either Pomc or the Mc4-r (4,5). Effects on glucose homeostasis also require activation of the Mc4-r (6). Thus a functional brain melanocortin circuit is required for 5-HT agonists to exert their effects on both energy balance and glucose metabolism. LOR decreases body weight in humans primarily by suppressing food intake without affecting energy expenditure (7-10). A pooled analysis of two randomized trials of 4008 and 3182 patients demonstrated that 47% of drug treated subjects achieved at least 5% wt loss (vs 23% for placebo) while 22% of subjects achieved at least 10% wt loss (vs 9% for placebo) (11). There were also differences in body fat, lipids and glycemic indicators. As with other drug therapies, there was a lot of individual variability in response to treatment such that 53% did not achieve clinically significant wt loss. There is evidence that greater than 5% wt loss at 12 wks can be used to predict the response to LOR at 1 yr (12). However given that there are now many choices for drug therapy it would be helpful to be able to predict long-term efficacy based on a biochemical profile or the acute feeding response to the drug. We propose to quantitate the extent to which POMC neurons are activated by LOR as a predictor of acute changes in feeding and long-term wt loss. The ability of acute changes in feeding behavior to predict long-term wt loss will also be studied. This approach has been used by our collaborator, [name], to demonstrate that the response to a laboratory meal after one wk treatment with phentermine was predictive of subsequent wt loss after 6 months of treatment (13). In addition to documenting the activation of hypothalamic POMC neurons it is also important to understand other neural or neuroendocrine consequences of drug treatment that would serve to attenuate the therapeutic effects of LOR. This protocol will focus on changes in the hypothalamic-pituitary-adrenal (HPA) axis and AgRP that could limit the effectiveness of LOR treatment. Serotonin agonists have well documented stimulatory effects on the HPA axis (14-17) but until recently the underlying mechanism has not been well

defined (18). The 5-HT2C R is highly expressed in CRH neurons in the hypothalamus and mediates the activation of these neurons by serotonin agonists with subsequent stimulation of pituitary ACTH and adrenal corticosterone release (18). The effects of LOR treatment on the HPA axis have not been reported. Given the potent stimulatory effects of glucocorticoids on food intake it is important to determine if treatment with LOR has acute and chronic effects on the HPA axis and if these effects impact the efficacy of drug treatment (19). We have previously found that measurements of intact POMC prohormone in cerebrospinal fluid (CSF) can serve as a marker of central POMC activity in humans; plasma AgRP has also emerged as a potential biomarker for brain AgRP. There are striking correlations of CSF POMC with BMI, adiposity, leptin and insulin; strong correlations of plasma AgRP with these parameters are also found. Furthermore, following short-term diet-induced weight loss, levels of CSF POMC and the POMC-derived peptide,  $\beta$ -endorphin ( $\beta$ -EP), decrease while CSF and plasma AgRP levels increase. We will therefore study the acute (1 wk) effects of LOR vs placebo on these biomarkers and on feeding behavior, in response to a laboratory test meal, as predictors of the longer-term (24-wk) response to LOR. Counterregulatory mechanisms that may limit the effectiveness of LOR treatment will be assessed by measurement of AgRP in CSF and plasma and of HPA activity. HPA activity will be characterized using plasma, salivary, urine and CSF measurements. The validation of biochemical markers (CSF and plasma neuropeptides) and behavioral markers (feeding response) that are predictive of drug efficacy would facilitate the choice of drug when initiating therapy. Furthermore understanding the counterregulatory responses that develop in response to weight loss and drug therapy could lead to interventions that improve drug efficacy.

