Subjects will be recruited for a 5-week crossover study with lorcaserin (LOR) and placebo followed by treatment with LOR or placebo for 24 weeks. **Phase 1:** Participants will be randomized to receive either LOR (10 mg bid) or placebo for 7 days followed by a 3 week washout period and will then be crossed over to receive 7 days of the other treatment (LOR or placebo). Thus each subject will be studied twice: once after receiving placebo and again after receiving lorcaserin. *Subjects will continue on a weight maintenance diet during this time to remain weight stable.* Salivary cortisol levels will be obtained at 0800h and at 2300h on days 2 and 6 of placebo and LOR. A 24h urine will be collected on day 6 of placebo and day 6 of LOR. On day 7 of both the placebo and LOR treatments, subjects will be studied in the clinical research center in the morning after an overnight fast. A lumbar puncture (spinal tap) will be performed and blood samples will be obtained. Subjects will then be fed a standardized breakfast (300 kcal). A laboratory test meal will be performed 4h later as described below. **Phase 2:** After completing the 7-day placebo and LOR studies, subjects will then be treated with LOR 10 mg bid (n= 40) for 24 weeks (Fig. 1). *Subjects will receive nutritional counseling to reduce their daily caloric intake to 600 kcal below their calculated caloric requirement and will be encourage to exercise moderately for 30 min daily.* Subjects will visit the clinic monthly during the 24 week study period for monitoring of vital signs and food counseling which will include review of food diaries. Salivary cortisol levels will be obtained the night before the monthly visits. Blood will be obtained at months 1, 2, 4 and 6 for safety monitoring and protein and hormone level analysis. At the end of the 24 week period subjects will be admitted to the GCRC for an LP followed by a fixed breakfast and a laboratory test meal 4h later. CSF will be tested for various proteins and hormones. Subjects will collect a 24h urine beginning the day before this final LP.

**Lumbar Puncture:** LP will be performed after an overnight fast by [name], Professor of Anesthesia and Director of Obstetrical Anesthesia, using a 25G Whitacre needle. 12 ml of CSF (approximately 2 teaspoons) will be removed at each LP.

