### **Statistical Procedures**

40 subjects will be recruited to account for a predicted 20% dropout rate in order to retain 32 subjects. For phase 1, the primary outcome is difference in food intake after 7 days of drug compared to placebo. Based on known acute changes in food intake after LOR a sample size of 24 subjects would be required using paired analysis (10). This sample size is more than adequate if CSF POMC is used as the primary outcome variable using a SD of 59 fmol/m (for overweight and obese subjects) to detect a 20% change in CSF POMC as has been reported for hypothalamic POMC in animals after treatment with 5-HT2cR agonists (23). However in order to use the outcomes of phase 1 to predict phase 2 wt loss, 40 subjects will be recruited to retain 32 and to achieve a range of wt loss as predicted by clinical trials (9). Food intake, including food energy and macronutrient consumption will be correlated with baseline POMC and AgRP levels. Differences in food intake at the placebo and LOR test meals will be correlated with changes in melanocortin peptide levels as well as with wt loss after 24 wks. Multiple regression modeling will be used to predict phase 2 wt loss in the LOR-treated participants from the within-subject difference between LOR and placebo test meal results and CSF POMC measurements from Phase 1. Bivariate Pearson correlation coefficients will be determined and stepwise multiple regression analyses will be performed to detect associations between POMC and AgRP and changes in levels following LOR and placebo with relevant variables: wt change, food intake, adiposity, leptin, sOB-R, insulin, HOMA-IR, gut hormones. Phase 1 is a double-blind trial with lorcaserin and placebo. After 10 subjects completed phase 1 the investigators were unblinded to the treatment of those 10 subjects in order to perform an interim analysis on the neuropeptide changes. We did detect a significant change in CSF POMC levels in the first 10 subjects but changes were not significant for other POMC derived peptide values. We would now like to unblind the next 10 subjects who have completed phase 1 in order to perform an interim analysis on the first 20 subjects as this may help with determining if we need additional POMC-derived study markers and optimization of assay conditions. The double blind will then continue for the subsequent study subjects.

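### Same-time correlations of phase 2 AgRP change with weight change cannot show that AgRP limits lorcaserin's effect; the forward prediction analysis should name AgRP and fix its timing

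*Combined protocol and SAP*

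**What the plan says.** Study Purpose and Rationale names two mechanisms that might blunt the drug. The first is AgRP: "Counterregulatory mechanisms that may limit the effectiveness of LOR treatment will be assessed by measurement of AgRP in CSF and plasma". The same sentence then adds HPA activity as the second. A few lines earlier the section describes what weight loss does to the markers: "following short-term diet-induced weight loss, levels of CSF POMC and the POMC-derived peptide" (beta-endorphin) "decrease while CSF and plasma AgRP levels increase". So AgRP appears both as a possible brake on weight loss and as something that rises when weight is lost.

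That section and the Scientific Abstract also state a forward intention: the one-week effects of lorcaserin against placebo on the markers are to serve as predictors of the 24-week response.

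Statistical Procedures contains two relevant analyses. A multiple regression predicts phase 2 weight loss from the within-person phase 1 contrast in the test meal and from CSF POMC; AgRP is not named. Separately, Pearson correlations and stepwise regressions are to "detect associations between POMC and AgRP and changes in levels following LOR and placebo with relevant variables: wt change", followed by food intake, adiposity and hormones. No marker time, direction or adjustment for weight already lost is given.

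Study Design keeps subjects weight stable in phase 1. Phase 2 adds counselling towards a 600 kcal daily deficit. Blood is drawn at months 1, 2, 4 and 6, and CSF again at week 24. On phase 2 treatment the section disagrees with itself: "subjects will then be treated with LOR 10 mg bid (n= 40) for 24 weeks" against "followed by treatment with LOR or placebo for 24 weeks". Those statements need to be reconciled.

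**The concern.** If AgRP limits efficacy, people with a larger AgRP rise should lose less weight: a negative association between AgRP rise and weight lost. If weight loss raises AgRP, people who lose more should show a larger rise: a positive association. An AgRP change measured during phase 2 or at week 24, set against weight lost by the same date, carries both.

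The observed sign then says little about a limiting effect. A real brake can be cancelled or reversed, and where there is none, a positive correlation shows only that weight was lost. The Scientific Abstract makes counterregulation one of the study's overall objectives, so a wrong-sign statement about AgRP would be a substantive error, although it would not touch the phase 1 primary outcome of food intake.

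**Working it through.** **Plan's own figure.** 40 recruited with 20% dropout: 32/(1 - 0.20) = 40, which reproduces. So n = 32 is used below.

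**Illustration 1.** The documents give no effect sizes for AgRP, so all coefficients are assumed, in SD units. A latent limiting tendency c has variance 1. Weight loss is W = -0.4c + sqrt(0.84)e. Week-24 AgRP change is A = c + kW + 0.7u, where k is the rise in AgRP per SD of weight lost and e, u are independent with variance 1.

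- cov(A, W) = k - 0.4
- var(A) = 1 + 0.49 + k² - 0.8k = 1.49 + k² - 0.8k
- k = 0: -0.4/sqrt(1.49) = -0.33
- k = 0.2: -0.2/sqrt(1.37) = -0.17
- k = 0.4: 0.00
- k = 0.6: +0.2/sqrt(1.37) = +0.17

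With no limiting effect, and the same AgRP noise, r = k/sqrt(1.49 + k²): 0.16, 0.31 and 0.44 for k = 0.2, 0.4 and 0.6.

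**Illustration 2, a two-way model.** L = u - bA and A = aL + v, error SDs 1; b is the limiting effect and a the effect of weight loss on AgRP. Solving, cov(A, L) = (a - b)/(1 + ab)², so the correlation depends on both coefficients and does not identify b. In 20,000 simulated trials of n = 32 with b = 0.5, mean r was -0.44, -0.17, 0.00, +0.14 and +0.31 for a = 0, 0.3, 0.5, 0.7 and 1. With b = 0 and a = 0.5 it was +0.44.

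**The phase 1 contrast.** It is taken while weight is held stable and before phase 2, so k (or a) does not enter it. In illustration 1 a phase 1 marker c + 0.7v gives r = -0.33 at every k. That constancy is built into the model, which assumes the 7-day change reflects the same tendency as later counterregulation.

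**Precision at n = 32** (Fisher z, two-sided 0.05).

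- Smallest detectable r: tanh((1.96 + 0.84)/sqrt(29)) = 0.48 at 80% power; 0.54 at 90%.
- Power for r = -0.33: atanh(0.33) × sqrt(29) = 1.85; 1.85 - 1.96 = -0.11, so about 45%.
- 95% interval around r = -0.33: tanh(-0.343 ± 0.364) = -0.61 to +0.02.
- In illustration 2, if the phase 1 change correlates 0.6 with v, mean r is about -0.26 and power about 32% (11% to 64% if that correlation is 0.3 to 0.9).

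**Cost of adjusting for early loss.** Extend illustration 1 to early loss W1 and later loss W2, each built like W, with residuals correlated q. Then corr(W1, W2) = 0.16 + 0.84q. Once W1 is adjusted for, k drops out and the partial correlation of early AgRP change with W2 is -0.328(1 - r12)/sqrt((1 - 0.107)(1 - r12²)), where r12 = corr(W1, W2). For q = 0.3, 0.5, 0.7 and 0.9 this gives -0.22, -0.18, -0.13 and -0.07. Without adjustment the covariance is -0.4 + k·r12, so the consequence of early loss leaks back in. Neither version alone is clean.

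**The case against.** The strongest reply is that the plan already looks forward. The rationale and abstract say that acute marker effects will be used as predictors of the 24-week response, and the markers include plasma AgRP. The association analysis speaks of changes after both treatments; on the text that puts everyone on lorcaserin in phase 2, placebo is given only in phase 1, so this wording fits phase 1 at least as well as week 24. That stands. A reader might infer that nothing in the plan places the marker before the weight loss; the documents do not support that. What remains is narrower: the intention does not reach the prediction model in Statistical Procedures, which omits AgRP, and the association analysis leaves timing open while phase 2 plasma and week-24 CSF are also collected.

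Second, the aim is to characterise responses that arise with weight loss and treatment, and measuring whether AgRP rises serves it. That is fair for description. But the rationale also presents AgRP as something that could limit effectiveness, and that claim needs more than a same-time correlation.

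Third, the premise concerns short-term diet-induced loss. Carrying it to phase 2 is an extrapolation, a reasonable one because a calorie deficit is prescribed.

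Fourth, the alternatives are weak at this sample size. That is true, and should be stated in the plan.

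**Conclusion.** The point holds for AgRP only. Same-time correlation of phase 2 or week-24 AgRP change with weight change cannot show that AgRP limits lorcaserin's effect, because the protocol's own premise makes weight loss a cause of the AgRP rise. Under the assumed models the correlation for one fixed limiting effect moves from -0.33 to +0.17, or from -0.44 to +0.31. The values are illustrative; the failure to identify the effect does not depend on the particular values chosen.

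A reader might go further and conclude that the whole counterregulation objective is unanswerable. The documents do not support that. HPA activity is the other named mechanism, and nothing in the text says weight loss alters it. POMC is mainly the marker of drug action. Phase 1 AgRP changes escape the problem, though they cannot show responses that arise only as weight falls.

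This is an inexpensive improvement to a secondary objective and leaves the primary outcome untouched.

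**What to change.** In Statistical Procedures:

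1. Name the phase 1 lorcaserin-minus-placebo difference in CSF and plasma AgRP as a predictor of 24-week weight loss, alongside the test-meal and CSF POMC terms.
2. As an exploratory analysis, relate plasma AgRP change at months 1 and 2 to the weight lost after that visit, with and without adjustment for weight already lost. State the reference sample; the phase 1 placebo draw is available.
3. Report week-24 AgRP changes, and their same-time correlation with weight change, as descriptive only and not as evidence that AgRP limits efficacy.

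Give every estimate with a confidence interval.

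The cost is a few sentences and a few regressions on samples already planned. Item 2 assumes that weight is recorded at the monthly visits, which the visit description does not list expressly.

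The plan should state the limits: about 32 completers give low power; phase 1 changes miss responses that develop only with weight loss; adjusting for early loss may remove part of the signal; and weight lost after month 2 probably spans a narrower range than the full 24-week loss.

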### **Scientific Abstract**

The overall objectives of this study are to validate biomarkers that can be used to predict responses to the weight loss medication, lorcaserin, and to characterize counterregulatory responses to drug therapy that may limit efficacy. Studies will focus on the hypothalamic melanocortin (MC) system, including the proopiomelanocortin (POMC)-derived MSH peptides, the MSH antagonist, agouti related protein (AgRP) and brain MC-Rs, which are key mediators of the central response to weight loss. Lorcaserin is a serotonin (5HT2cR) agonist that works primarily by activation of POMC neurons and melanocortin signaling. We have found that measurements of the POMC prohormone in cerebrospinal fluid (CSF) can serve as a marker of central POMC activity in humans; plasma AgRP measurements have also emerged as a potential biomarker of brain AgRP activity. The current protocol will examine the acute (1 wk) effects of lorcaserin vs placebo on these biomarkers and on feeding behavior, in response to a laboratory test meal, as predictors of the longer-term (24-wk) response to lorcaserin. Counterregulatory mechanisms that may limit the effectiveness of lorcaserin treatment will also be characterized with a focus on the hypothalamic-pituitary-adrenal (HPA) axis and changes in AgRP levels. 60 healthy male and female subjects age 18-60 yr (BMI 28-42) will be recruited for a 5-wk double-blind crossover study with lorcaserin and placebo followed by treatment with lorcaserin or placebo for 24 wks. Participants will be randomized to receive either lorcaserin or placebo for 7 days followed by a 3 wk washout period and will then be crossed over to receive 7 days of the other treatment. On day 7 of both the placebo and lorcaserin treatments, subjects will be studied in the morning after an overnight fast in the clinical research center. A lumbar puncture (LP) will be performed to obtain CSF and blood samples will be obtained. Subjects will then be fed a standardized breakfast (300 kcal). A laboratory test meal will be performed 4h later. After completing the 7 day placebo and lorcaserin studies, subjects will then be continued on lorcaserin (n= 40) for 24 wks. Subjects will receive nutritional counseling to reduce their daily caloric intake to 600 kcal below their calculated caloric requirement and will be encouraged to exercise moderately for 30 min daily. Subjects will visit the clinic monthly during the 24 wk study period for counseling and to review food diaries; vital signs and safety labs will be monitored. Blood will be obtained for AgRP and hormone levels. At the end of the 24 wk period subjects will be admitted to the clinical research center for an LP followed by a

fixed breakfast and a laboratory test meal 4h later. CSF and blood will be assayed for a melanocortin peptides and hormones. The validation of biochemical markers (CSF and plasma neuropeptides) and behavioral markers (feeding response) that are predictive of drug efficacy would facilitate the choice of drug when initiating therapy. Furthermore understanding the counterregulatory responses that develop in response to weight loss and drug therapy could lead to interventions that improve drug efficacy.

### **Statistical Procedures**

40 subjects will be recruited to account for a predicted 20% dropout rate in order to retain 32 subjects. For phase 1, the primary outcome is difference in food intake after 7 days of drug compared to placebo. Based on known acute changes in food intake after LOR a sample size of 24 subjects would be required using paired analysis (10). This sample size is more than adequate if CSF POMC is used as the primary outcome variable using a SD of 59 fmol/m (for overweight and obese subjects) to detect a 20% change in CSF POMC as has been reported for hypothalamic POMC in animals after treatment with 5-HT2cR agonists (23). However in order to use the outcomes of phase 1 to predict phase 2 wt loss, 40 subjects will be recruited to retain 32 and to achieve a range of wt loss as predicted by clinical trials (9). Food intake, including food energy and macronutrient consumption will be correlated with baseline POMC and AgRP levels. Differences in food intake at the placebo and LOR test meals will be correlated with changes in melanocortin peptide levels as well as with wt loss after 24 wks. Multiple regression modeling will be used to predict phase 2 wt loss in the LOR-treated participants from the within-subject difference between LOR and placebo test meal results and CSF POMC measurements from Phase 1. Bivariate Pearson correlation coefficients will be determined and stepwise multiple regression analyses will be performed to detect associations between POMC and AgRP and changes in levels following LOR and placebo with relevant variables: wt change, food intake, adiposity, leptin, sOB-R, insulin, HOMA-IR, gut hormones. Phase 1 is a double-blind trial with lorcaserin and placebo. After 10 subjects completed phase 1 the investigators were unblinded to the treatment of those 10 subjects in order to perform an interim analysis on the neuropeptide changes. We did detect a significant change in CSF POMC levels in the first 10 subjects but changes were not significant for other POMC derived peptide values. We would now like to unblind the next 10 subjects who have completed phase 1 in order to perform an interim analysis on the first 20 subjects as this may help with determining if we need additional POMC-derived study markers and optimization of assay conditions. The double blind will then continue for the subsequent study subjects.

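### The randomised crossover is analysed with no period or sequence term, so a visit-order shift could create or hide intake–peptide correlations and distort single coefficients in the weight-loss regressions

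*Combined protocol and SAP*

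**What the plan says.** Study Design sets up a two-period crossover: "Participants will be randomized to receive either LOR (10 mg bid) or placebo for 7 days followed by a 3 week washout period", after which each subject receives the other treatment. The Scientific Abstract describes the same design.

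Statistical Procedures then names four kinds of analysis:

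- A paired comparison, mentioned only in the sample-size sentence: "a sample size of 24 subjects would be required using paired analysis".
- Correlation of one LOR–placebo difference with another: "Differences in food intake at the placebo and LOR test meals will be correlated with changes in melanocortin peptide levels". The intake difference is also to be correlated with 24-week weight loss.
- A multiple regression predicting phase 2 weight loss "from the within-subject difference between LOR and placebo test meal results and CSF POMC measurements from Phase 1".
- A wider search: "Bivariate Pearson correlation coefficients will be determined and stepwise multiple regression analyses will be performed to detect associations".

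The variables listed for that search are weight change, food intake, adiposity, leptin, sOB-R, insulin, HOMA-IR and gut hormones. Period, visit order and sequence are not among them, and no other section supplies such a term. The plan does not say that the analyses are unadjusted, but an analyst who followed it as written would not adjust.

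**The concern.** Suppose subjects eat differently at their second buffet than at their first, whatever the drug. Those who take LOR second then have the shift added to their LOR–placebo difference, and those who take it first have it subtracted. If a peptide also shifts, sequence becomes a common cause of both differences. Equal sequence sizes protect the mean difference but not a correlation between two differences.

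This bears on a stated aim: "We propose to quantitate the extent to which POMC neurons are activated by LOR as a predictor of acute changes in feeding". The expected signal is a negative correlation (POMC up, intake down). Shifts in opposite directions imitate it, and shifts in the same direction hide it.

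The weight-loss regression is exposed by the same route. If POMC enters as a LOR–placebo difference, the intake and POMC predictors share the same sequence error. The study wants to know which marker predicts response, so a coefficient that is wrong because of that shared error matters.

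**Working it through.** **Inputs from the documents.** Recruited 40, predicted dropout 20%, retained 40 × 0.80 = 32, which reproduces the plan's figure. (The Scientific Abstract gives 60 recruited; I use the 32 of Statistical Procedures.) The paired sample size is 24. It cannot be reproduced, because no effect size, SD of the difference, alpha or power is stated.

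**Assumptions.** k is the shift from visit 1 to visit 2 divided by the within-sequence SD of the LOR–placebo difference. It is unknown, so a range is shown. For scale: if 24 subjects give 80% power in a two-sided 5% paired t test, the drug effect is 0.597 SD, so k = 0.25 is 0.25/0.597 = 0.42 of it and k = 0.5 is 0.84 of it. Sequences are 16/16 unless stated.

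**Model.** Difference = drug effect + s·k + error, with s = +1 for LOR second, s = -1 for LOR first, and error SD 1.

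**1. Intake difference against peptide difference.** With true within-sequence correlation ρ and shifts k_F and k_P, the unadjusted correlation tends to

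(ρ + k_F·k_P) / √[(1 + k_F²)(1 + k_P²)].

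For ρ = 0 and k = 0.5 in both: 0.25/1.25 = 0.20. For ρ = -0.50 with the same shifts: (-0.50 + 0.25)/1.25 = -0.20. Simulation at n = 32, same-direction shifts:

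| Shifts (intake, peptide) | Type I error, ρ = 0 | Power, ρ = -0.50 |
|---|---|---|
| 0, 0 | 5.0% | 0.85 |
| 0.1, 0.1 | 5.0% | 0.83 |
| 0.25, 0.25 | 6.2% | 0.66 |
| 0.25, 0.5 | 9.1% | 0.44 |
| 0.5, 0.5 | 20% | 0.16 |
| 0.5, 0 | 5.0% | 0.75 |
| Any of these, sequence adjusted | 5% | 0.84 |

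If only one measure shifts, k_F·k_P = 0: the correlation is diluted, with no excess of false positives.

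**2. Weight loss on the intake and POMC differences together.** Standardise weight loss, let intake have slope b and POMC slope 0, let the true differences be uncorrelated, and give both the same shift k. The POMC coefficient then tends to -b·k²/(1 + 2k²). With b = 0.6 and k = 0.5 this is -0.6 × 0.25/1.5 = -0.10 instead of 0; its sign reverses if the shifts are opposite. The intake coefficient falls to 0.50, and R² from 0.36 to 0.6 × 0.50 = 0.30. In simulation at n = 32 the POMC term is falsely significant in about 5–6% of trials at k = 0.25 and 9–11% at k = 0.5 (true intake correlation 0.5 to 0.6), against about 5% with sequence in the model.

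**3. Intake difference against weight loss, bivariate.** If weight loss does not depend on sequence, the correlation is multiplied by 1/√(1 + k²). A true 0.50 becomes 0.49 (k = 0.25) or 0.45 (k = 0.5), with power 0.83 or 0.75 against 0.84 adjusted. This is dilution. If weight loss also differs by ±g SD between sequences, a false correlation of k·g/√[(1 + k²)(1 + g²)] appears. At k = 0.5 and g = 0.25 it is 0.125/√(1.25 × 1.0625) = 0.11.

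**4. Phase 1 mean.** At 16/16 there is no bias. Power is 0.895 (k = 0.25) or 0.856 (k = 0.5), against 0.905 adjusted. With completers split 18/14, the raw mean moves by k × (18 - 14)/32 = 0.125k, that is 0.031 or 0.063, about 5% or 10% of 0.597. If 40 start 20/20 (assumed) and 8 leave regardless of sequence, a split at least that uneven has probability 0.24.

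**The case against.** The best defence is that nothing in the documents reports or suggests a period effect, and Study Design works against one: "Subjects will continue on a weight maintenance diet during this time to remain weight stable", with an overnight fast, the same 300 kcal breakfast, a fixed buffet and a three-week washout. A false intake–peptide correlation needs both an eating measure and a peptide to move with visit order. The striking figures need k = 0.5 in both, which is most of the assumed drug effect; at k = 0.25 type I error is only 6%. The primary phase 1 comparison is barely touched, and none of the stated sample sizes (24, 32, 40) depends on the point. A paired analysis does not rule out a period term, so this may be brevity rather than a choice.

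Most of that stands, and it keeps the point at a modest weight. It does not remove it: standardised conditions limit a shift without excluding one, and power for a true -0.50 already drops from 0.84 to 0.66 at k = 0.25 when both shifts run the same way.

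Two stronger conclusions might be inferred, and the documents support neither. One is that phase 1 results are, or will be, distorted: no period effect is reported, and the mean is unbiased when the completing sequences are equal in size. The other is that weight-loss prediction can only be diluted, leaving the intake–peptide correlation as the only place where a false result can arise. That fails because the plan uses multiple and stepwise regression, where predictors can share the sequence error. It also assumes that weight loss is unrelated to sequence. Study Design states no washout before phase 2, and the Scientific Abstract speaks of continuing on the drug, so subjects who take LOR second may enter phase 2 directly from it.

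**Conclusion.** The omission is clear from the text; the size of the harm is conditional. If both measures shift with visit order, intake–peptide correlations can be created or hidden: type I error 6% to 20%, and power for -0.50 down to 0.66 or 0.16, for k from 0.25 to 0.5 in both. If POMC enters the weight-loss regression as a difference, a null POMC term is falsely significant in up to 9–11% of trials over the same range. The plan's wording does not settle whether it enters that way.

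Only the bivariate weight-loss correlation and the overall R² are merely diluted, and only if weight loss does not depend on sequence. The phase 1 mean loses a little power, with bias only if the completing sequences are unequal.

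All of this rests on assumed k, normal differences and 32 completers. At k = 0.1 adjustment gains practically nothing. This is a cheap improvement worth considering, not a flaw that undermines the trial.

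**What to change.** - Analyse each phase 1 outcome with treatment and period as fixed effects and subject as random. For completers, an equivalent is to regress the LOR–placebo difference on sequence coded +1/2 and -1/2 and test the intercept. Mean-centring the code would return the raw mean. The two approaches differ if some subjects complete only one period.
- Report the period effect with its 95% CI. At n = 32 the half-width for k is t(30)/√32 = 0.36.
- Report partial correlations given sequence wherever a LOR–placebo difference is used.
- Force sequence into the phase 2 and stepwise regressions, and state whether POMC enters as a difference.
- Do not adjust only after a significant period test: at n = 32 that test has power 0.28 for k = 0.25 and 0.78 for k = 0.5.
- Date and justify the change as made after unblinded data were seen. The plan records that "After 10 subjects completed phase 1 the investigators were unblinded to the treatment of those 10 subjects" and asks to unblind the next 10; note those too if that has happened.

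The cost is wording and one degree of freedom. With no period effect, power for a correlation of 0.50 goes from 0.85 to 0.84, and phase 1 power stays at about 0.905 at 16/16 (0.906 to 0.902 at 18/14).
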